6.3 Other Study Related Definitions

Analytical Study Week Assignments

Analytical windows will be used to assign parameter measurements to study weeks. The algorithm is provided in Appendix A.

Actual Treatment Group

A subject's actual treatment group is the randomized treatment group, unless the subject receives treatment throughout the double-blind period that is different from the randomized treatment group assignment, in which case the actual treatment group is the treatment received.

Investigational Product (IP)

Double-blind period IP: evolocumab SC 420 mg QM and corresponding SC placebo. Open-label period IP: evolocumab SC 420 mg QM

Double-blind IP Exposure Period in Months

For each subject:

Double-blind IP Exposure Period = [min (TR01EDT

-1, EOIP + 28 days, EOS Date) - Study day 1 + 1]/ 365.25 * 12

Open-label IP Exposure Period in Months

For each subject receiving at least one dose of open-label IP:

Open-label IP Exposure Period = [min (EOIP + 28 days, EOS Date) - TR02SDT + 1]/365.25 * 12

Study Exposure Period in Months

For each randomized subject, Study Exposure Period = (EOS date – Enrollment Date + 1) / 365.25 * 12

Treatment Emergent Adverse Event (TEAE)

Events categorized as Adverse Events (AEs) starting on or after first dose of investigational product as determined by the flag indicating if the adverse event started before the first dose on the Events eCRF and up to and including EOS. Double-blind TEAEs are those that start before the earlier of last dose date of double blind

Statistical Analysis Plan: 20130286

Date: 20 January 2019 Page 16 of 35

IP + 28 days and first dose date of open-label IP. Open-label TEAEs are those that start on or after the date of first dose of open-label IP and start before the earlier of last dose date of open-label IP + 28 days and EOS.

Serious Adverse Event (SAE)

Treatment-emergent adverse events (as defined above) that are indicated as serious on the Events eCRF.

LDL-C Reflexive Approach

For all analyses related to LDL-C, unless specified otherwise, a LDL-C reflexive approach will be used. When calculated LDL-C is less than 40 mg/dL or triglycerides are > 400 mg/dL, the UC LDL-C value from the same blood sample will be used instead, if available.

Achievement of target LDL-C < 70 mg/dL

A subject has achievement of LDL-C < 70 mg/dL if the week 24 LDL-C value is less than 70 mg/dL. If the value is missing, the subject is considered without the achievement.

LDL-C response (50% reduction from baseline)

A subject has a response of 50% reduction from baseline in LDL-C if the week 24 LDL-C percent change from baseline value is less than or equal to -50%. If the value is missing, the subject is considered without the response.

7. Analysis Subsets

7.1 Full Analysis Set

The full analysis set (FAS) includes all randomized subjects who received at least 1 dose of IP. This analysis set will be used in both efficacy and safety analyses. In efficacy analysis, subjects will be analyzed according to their randomized treatment group assignment. For safety analyses, subjects will be grouped according to their actual treatment group (as defined in Section 6.3).

7.2 Completers Analysis Set

The completer analysis set (CAS) includes subjects in the FAS who adhered to the scheduled IP regimen in the double-blind treatment period and have an observed value for the primary endpoint. Subjects who did not adhere are identified as those who have an EOIP reason other than completed and EOIP date not after first dose of open-label IP.

Statistical Analysis Plan: 20130286

Date: 20 January 2019 Page 17 of 35

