6.2.1.2 Double-blind Treatment Period

The IP (420 mg evolocumab or matching placebo via AMD, or Al/pen) will be administered QM on day 1, week 4, week 8, week 12, week 16, and week 20.

SC evolocumab and placebo will be administered at the study site or in an appropriate non-clinic setting (eg, at the subject's home). Observed, in-clinic dosing should occur at day 1 and week 20. Subjects who do not wish to self-inject at home may return to the clinic for injection. See Table 3 for the schedule of in-clinic visits.

The IP will be administered SC in accordance with instructions in the IPIM and the Information for Use (IFU). The subject (or designee, if not a qualified healthcare professional) must have demonstrated competency, as per site judgment, at administration of SC injections before self-administration is permitted: the first

Protocol Number: 20130286

Page 25 of 73 Date: 30 January 2017

self-administered dose by the subject (or designee, if not a healthcare professional) must be administered at the site under the supervision of a healthcare provider. If IP is to be administered during the study visit, administration must occur after all other procedures have been completed.

When IP is mandated to be administered at the study site, the date and time of administration, the body location of the injection, and whether the injection was administered fully, partially, or not at all, in addition to the reason for a partial/lack of injection, are to be provided. When IP can be administered at an appropriate non-clinic setting (eg, at the subject's home), at a minimum, the dates the devices were dispensed and returned, the number of devices dispensed and returned, and number of devices administered fully, partially, or not at all, in addition to the reason for a partial/lack of injection, must be provided.

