When IP is mandated to be administered at the study site, the date and completion time of administration, the body location of the injection, and whether the injection was administered fully, or partially, or not at all administered, in addition to the reason for a partial/lack of injection, are to be recorded on each subject's CRF provided. When IP can be administered at an appropriate non-clinic setting (eg, at the subject's home), a non-investigator site location, at a minimum, the dates that the devices were dispensed and the used devices were returned, the number of devices dispensed and returned, and number of devices administered fully, partially, or not at all, in addition to the reason for a partial/lack of injection, must be provided whether each device was returned fully or partially used are to be recorded on each subject's CRF.

Overdose with this product has not been reported.

6.2.1.3 **Open-label Period**

Product: Evolocumab

Subjects who receive a dose of IP at week 20 will continue in an open-label period. During the open-label period, all subjects will be treated with 420 mg evolocumab via AMD, or Al/pen. Dosing at week 24 is expected to be in-clinic while dosing for weeks 28, 32, 36, 40, 44, and 48 is expected to be in an appropriate non-clinic setting (eg, at the subject's home, even on weeks with in-clinic visits); however, subjects who do not wish to self-inject at home may return to the clinic for injection.

Protocol Number: 20130286

Date: 30 January 2017

Page 26 of 73

6.2.2 Dosage Adjustments, Delays, Rules for Withholding or Restarting,

No dose adjustments are allowed in this study. If, in the opinion of the investigator, a subject is unable to tolerate a specific dose of IP, that subject will discontinue IP but will continue to return for all other study procedures and measurements until the EOS visit.

If a dose of evolocumab is missed, administration should occur as soon as possible if there are > 7 days until the next scheduled dose. If there are less than 7 days before the next scheduled dose, the missed dose should be omitted and the next dose should be administered according to the original schedule.

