6.1 Study Time Points

Enrollment Date

Enrollment Date is the same as randomization date (ie, the date a subject is randomized in the interactive voice response system (IVRS) as recorded on the eCRF).

Statistical Analysis Plan: 20130286

Study Day 1

For each subject, Study Day 1 is defined as the first day of investigational product administration (SC evolocumab 420 mg QM or SC placebo QM). If a subject enrolled but never received IP, Study Day 1 is defined as the enrollment day.

Study Day

For each subject, and for a given date of interest, study day is defined as the number of days since Study Day 1:

Study day = (date of interest – Study Day 1 date) + 1.

If the date of interest is prior to the Study Day 1:

Study day = (date of interest – Study Day 1 date), so that the day prior to Study Day 1 is study day -1.

First Dose Date of SC IP (TR01SDTM)

For each subject, the first dose date of SC IP is defined as the first date of investigational product administration, equivalent to study day 1.

First Dose Date of SC IP in the Open-label period (TR02SDTM)

For each subject, the first dose date of SC IP in the open-label period is defined as the first date of open-label investigational product administration.

Last dose date of Double-blind Investigational Product

For each subject, the last dose date of double-blind investigational product is defined as the date of the last administration of double-blind investigational product.

End of Investigational Product (EOIP) Date

For each subject, the end of investigational product date is defined as the date of decision to end investigational product.

End of Study (EOS) Date

For each subject, the End of Study Date is the date recorded on the End of Study eCRF.

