10.5.1.3 Covariate and Subgroup Analyses of Primary Endpoints

As a supportive analysis, the primary analysis will be repeated using the CAS to estimate the on-treatment treatment effect.

In addition to the primary analysis specified in Section 10.5.1.1, covariate-adjusted analyses of the primary efficacy endpoint will be performed as supportive analyses using the baseline covariates in Section 4.2 in their original format, one at a time, in the primary model used in the primary analyses as appropriate.

Statistical Analysis Plan: 20130286

Date: 20 January 2019 **Page 27 of 35**

Subgroup analyses on the primary efficacy endpoint will be conducted using the subgroups specified in Section 7.3. Depending on the distribution of baseline LDL-C, analyses using different subgroups of baseline LDL-C will be performed if applicable. Treatment effect differences among subgroups, which represent subgroup by treatment interactions, will be estimated and tested based on statistics from the subgroup repeated measures models.

For covariate and subgroup analyses, the stratification factors from the eCRF will be used. Differences in stratum assignment between data collection via IVRS and eCRF will be tabulated.

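### IP exposure ends at the decision to stop IP plus 28 days, not the last dose plus 28 days, and the completer set's adherence rule takes no account of missed or partial doses

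*SAP*

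**What the plan says.** **Exposure.** SAP 6.1 states that "the end of investigational product date is defined as the date of decision to end investigational product". SAP 6.3 then gives "Open-label IP Exposure Period = [min (EOIP + 28 days, EOS Date") minus TR02SDT plus 1, converted to months. The double-blind formula is the minimum of three terms (TR01EDT - 1, EOIP + 28 days, EOS date), counted from Study Day 1. TR01EDT is not defined in the SAP text available. The treatment-emergent adverse event (TEAE) windows, also in SAP 6.3, use the last dose date + 28 days. SAP 6.1 separately defines a last double-blind dose date, but neither exposure formula refers to it by that name.

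**Completer set.** SAP 7.2 describes the CAS as "subjects in the FAS who adhered to the scheduled IP regimen in the double-blind treatment period" with an observed primary endpoint value. Its working rule is "Subjects who did not adhere are identified as those who have an EOIP reason other than completed and EOIP date not after first dose" (the first open-label dose is meant). SAP 10.5.1.3 says that "the primary analysis will be repeated using the CAS to estimate the on-treatment treatment effect".

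**Dosing.** Protocol 6.2.2 has a missed dose given as soon as possible if more than 7 days remain before the next one. With less than 7 days left, "the missed dose should be omitted and the next dose should be administered according to the original schedule". Protocol 6.2.1.3 makes the week 20 dose the condition for open-label entry. For dosing outside the clinic, Protocol 6.2.1.2 says that the "number of devices administered fully, partially, or not at all, in addition to the reason for a partial/lack of injection, must be provided".

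**The concern.** Two derivations rest on the end-of-IP record where the quantity wanted depends on doses.

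For exposure, a subject may stop dosing some time before the decision to end IP is made. Four of the six double-blind doses and the open-label doses after week 24 are expected outside the clinic, and the open-label visits after week 24 are only at weeks 36 and 52 (Protocol Table 3). A subject who stops IP for intolerance stays in the study to EOS (Protocol 6.2.2), so the EOS term need not cap the interval soon. Exposure can then run past the point where SAP 6.3 stops counting that subject's events.

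For the CAS, not having formally stopped IP is a different thing from having followed a six-dose schedule. The primary analysis deliberately uses LDL-C values on or off IP. The CAS repeat is the contrast meant to show the on-treatment effect, and its rule does not deliver the set that its definition describes.

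**Working it through.** No sample size, power or alpha figure is in dispute, so there is no stated result to reproduce. The check applies the SAP's rules to example subjects.

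**Inputs.** Day = 7 x week + 1 (SAP Appendix A), so weeks 4, 8, 12, 20, 24, 36, 40 and 52 are days 29, 57, 85, 141, 169, 253, 281 and 365. Months = days / 365.25 x 12. EOS is day 365 and TR02SDT is day 169. *Assumption:* the decision falls on the day shown; the documents do not tie it to a visit.

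**Open-label exposure.** SAP: min(decision + 28, 365) - 169 + 1. Comparison: min(last dose + 28, 365) - 169 + 1.

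| Last dose | Decision | SAP | Last dose + 28 | Excess |
|---|---|---|---|---|
| Week 24 | Week 36 | 281 - 169 + 1 = 113 days (3.71 months) | 197 - 169 + 1 = 29 days (0.95) | 84 days |
| Week 36 | Week 40 | 309 - 169 + 1 = 141 days (4.63) | 281 - 169 + 1 = 113 days (3.71) | 28 days |
| Week 48 | Week 52 | 365 - 169 + 1 = 197 days (6.47) | same, capped by EOS | 0 |

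The excess is the decision date minus the last dose date, limited by EOS. It is zero if both fall on the same day.

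**Double-blind exposure.** The result depends on what TR01EDT means.

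- *If it means the first open-label dose date:* an early stopper with no open-label dose has no value for that term, and EOIP + 28 applies. Last dose week 4 with decision week 12 ends at 85 + 28 = 113 instead of 29 + 28 = 57, an excess of 56 days. Last dose week 8 with decision week 20 ends at 169 instead of 85, or 5.55 months against 2.79.
- *If it means the last double-blind dose date* (by analogy with TR01SDTM, the first dose date): a fully dosed subject ends at 141 - 1 = 140, which is 140 days or 4.60 months. Ending the day before the first open-label dose gives 168 days or 5.52 months. A one-dose subject gets (1 - 1) - 1 + 1 = 0. Exposure is understated.

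**CAS rule.** Fix the day 1 dose (needed for the FAS) and the week 20 dose (needed for open-label entry). The four doses at weeks 4 to 16 then have 2^4 = 16 taken-or-missed patterns. For a subject who enters open-label without formally stopping IP and has a week 24 value, the rule keeps all 16, down to 2 of 6 doses. Full dosing is 1 of the 16.

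*Assumption, since the documents give no rate:* if each of these four doses is missed independently with probability p, the share missing at least one is 1 - (1 - p)^4, or 8%, 19% and 34% for p = 2%, 5% and 10%.

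**Dilution at week 24.** Dilution = 40 x share of evolocumab CAS subjects with missed doses x fraction of effect lost, where 40 is the effect assumed in SAP 3.2. With assumed shares of 5% to 20% and losses of 0% to 50%, it runs from 0 to 40 x 0.20 x 0.50 = 4 points.

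**The case against.** It can fairly be said that little depends on either rule. The primary analysis is on the FAS and uses LDL-C values regardless of IP status, and the CAS is labelled supportive. Exposure is summarised descriptively, adverse events are reported as subject incidence, and no exposure-adjusted rate is planned in the text available. SAP 10.6.5 also plans a summary of dose received. Excluding formal discontinuers is an explicit, prespecified rule, and a stricter dose-based set brings more post-randomisation selection. All of this stands, and it limits the consequences. It does not make the rule match the definition in SAP 7.2, and the dose-received summary has no stated categories and does not feed the CAS.

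Three stronger readings are tempting and are not supported:

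- **Heavy dilution from subjects who missed the last dose.** Open-label entrants had the week 20 dose, so the retained non-adherers are mainly those who missed doses at weeks 4 to 16 and were dosed again four weeks before the endpoint. A late missed dose is also first to be made up where time allows, not simply dropped.
- **A certain overrun in the double-blind period.** It occurs under one meaning of TR01EDT and reverses under the other.
- **Overruns of 8 to 12 weeks as typical.** EOIP is the date of the decision, not of the visit at which it is recorded, so the longer examples hold only if the decision came that late.

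**Conclusion.** The point holds as two limited faults.

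1. **Exposure.** For subjects who stop IP early and stay in the study, open-label exposure is overstated by the time from last dose to decision, capped by EOS: 0 to 84 days in the examples. Week 52 completers whose last dose was at week 48 are unaffected. Double-blind exposure cannot be settled until TR01EDT is defined: under one reading it overruns in the same way, and under the other it falls short.
2. **CAS.** The rule removes formal early stoppers only, so subjects with missed or partial doses at weeks 4 to 16 remain in a set described as adherent. The effect on the week 24 estimate is probably small, about 0 to 4 points against an assumed 40, under assumed shares and losses that the documents neither give nor exclude.

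The primary efficacy conclusion is not at risk. What needs correcting is a mismatch between stated definitions and the rules that implement them.

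**What to change.** **Exposure (SAP 6.3).** Anchor both formulas on the last dose date, as the TEAE windows already are, and name each term:

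- Double-blind = min(first open-label dose - 1, last double-blind dose + 28, EOS) - Study Day 1 + 1.
- Open-label = min(last open-label dose + 28, EOS) - TR02SDT + 1.

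This also removes the undefined TR01EDT.

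**CAS (SAP 7.2).** Either derive adherence from the recorded full, partial or missed administrations, with a threshold that the sponsor states in advance (all six double-blind doses is one example; the documents do not dictate a cut-off), or keep the present rule and relabel the set as subjects who did not discontinue IP, with SAP 10.5.1.3 reworded to match.

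**Cost.** SAP wording and derivation code; the protocol already requires the dosing data to be collected. A dose-based CAS would be somewhat smaller and more selected after randomisation, which should be said when it is reported. Relabelling avoids that cost but leaves no analysis restricted to subjects who followed the dosing schedule.

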7.3 Long-term Analysis Set

The long-term analysis set (LAS) will include all subjects who received at least 1 dose of open-label IP in the open-label period. This analysis set will be used in all analyses for the open-label period.

7.4 Subgroup Analyses

Subgroup by stratification factor

- Statin use at baseline (yes/no)
- Hepatitis C Status (yes/no)

Subgroup by baseline characteristics

- Age: < 65 years, ≥ 65 years
- Sex
- Race (black, white, and other)
- LDL-C: (< baseline median, ≥ baseline median)
- Family history of premature CHD (yes, no)
- Region (North America, Europe, other)
- BMI (<25, 25-30, ≥30)
- Hypertension (yes, no)
- Current smoker (yes, no)
- Baseline CHD risk factors ≥ 2 (yes, no)
- Triglicerides (< baseline median, ≥ baseline median)
- NCEP high risk (yes, no)
- Statin intensity (High/Moderate/Low intensity as per ACC/AHA guidelines)
- Lipid entry target (above both non-HDL-C and LDL-C entry criteria thresholds, above non-HDL-C entry criteria threshold only, and above LDL-C criteria threshold only)
- Glucose tolerance status (type 2 diabetes mellitus, metabolic syndrome, neither type 2 diabetes mellitus nor metabolic syndrome)
- Protease inhibitor use

8. Interim Analysis and Early Stopping Guidelines

No interim analysis is planned for this study.

9. Data Screening and Acceptance

9.1 General Principles

The objective of the data screening is to assess the quantity, quality, and statistical characteristics of the data relative to the requirements of the planned analyses.

Statistical Analysis Plan: 20130286

Date: 20 January 2019 **Page 18 of 35**

9.2 Data Handling and Electronic Transfer of Data

The Amgen Global Study Operations-Data Management (GSO-DM) department will provide all data to be used in the planned analyses. This study will use the RAVE database.

All data collected in the eCRF will be extracted from RAVE. Protocol deviations will be transferred from eClinical. Unblinded subject and box ID randomization lists will be provided by Amgen's randomization group and the IVRS when the study stops. Details on data transfer will be provided in the Data Transfer Plan.

9.3 Handling of Missing and Incomplete Data

9.3.1 Patterns of Missing Data

Subjects may be missing specific data points for various reasons. In general, data may be missing due to a subject's early withdrawal from study, a missed visit, or non-evaluability of a data point or an endpoint at a particular point in time. In the Data issue identification and resolution (DIIR) process, queries will be made to the sites to distinguish true missing values from other unknown values (eg, due to measurement or sample processing error). All attempts will be made to capture missing or partial data for this trial prior to the database lock.

The frequency and pattern of missing data for efficacy endpoints will be assessed through descriptive summaries of the measurements over time.

9.3.2 Missing Lipid Measurements

For efficacy endpoints, where the analysis method uses a repeated measures linear effects model, missing lipid measurements will not be imputed. The handling of missing LDL-C response (50% reduction of week 24 LDL-C from baseline) and achievement of target week 24 LDL-C < 70 mg/dL is provided in Section 6.3. Sensitivity analysis will be performed on the primary endpoint to evaluate the robustness of the missing at random assumption used in the repeated measures linear effects model, details are provided in section 10.5.1.2.

9.3.3 Handling of Incomplete Dates

Adverse events can be flagged as treatment emergent using valid answers to the question "Did event start before first dose of investigational product?" on the eCRF regardless of the AE onset date being complete or not.

Adverse events and concomitant medication ([eg, lipid regulatory medication] collected start date data) with completely or partially missing start dates will be queried. After the

Statistical Analysis Plan: 20130286

Date: 20 January 2019 Page 19 of 35

issue is queried, if the date is still incomplete with year only or year and month only, the start date will be imputed as described in Table 1 below.

Table 1. Imputation Rules for Incomplete Dates

	Missing	Imputation	Exception
Start date (AE and concomitant medication)	Day	1	Default to Study Day 1 if an event starts the same year and month as Study Day 1
,	Day / Month	1-Jan	Default to Study Day 1 if an event started the same year as Study Day 1

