7.1 Schedule of Assessments

Product: Evolocumab

Screening assessments and study procedures are outlined in this section and in Table 3 (Schedule of Assessments).

Product: Evolocumab
Protocol Number: 20130286
Date: 30 January 2017

Date: 30 January 2017 Page 33 of 73

Table 3. Schedule of Assessments

		Double-Blind Period				Open-Label Period		
Study Day / Timepoint	Screening 4 (± 1) weeks	Day 1	Week 12 ± 3 days	Week 20 ± 3 days	Week 24 ± 3 daysª	Week 36 ± 7 days	EOS Week 52 ± 7 days	
General Procedures								
Informed consent	Х							
Medical history	Х							
Vital signs	Х	Х	Х	Х	Х	Х	Х	
Safety data reporting ^b	Х	Х	Х	Х	Х	Х	Х	
Concomitant therapy	Х	Х	Х	Х	Х	Х	Х	
Physical exam	Х	Х			Х		Х	
Body weight, waist circumference	Х				Х		Х	
Body height	Х							
Screening placebo injection ^c	Х							
Randomization		Х						
Central Laboratory								
Fasting lipids, ApoA1, ApoB, Lp(a)	X	Х	Х		Х	Х	Х	
		Х	Х		Х	Х	Х	
		Х	Х		Х	Х	Х	
HIV viral load and CD4	Х	Х	Х		Х	Х	Х	
Hepatitis C antibodies	X							
Hepatitis C viral load ^d	Х	Х	Х		Х	Х	Х	
Chemistry	X	Х	Х		Х	Х	Х	

Page 1 of 2

Footnotes defined on next page of this table

Product: Evolocumab
Protocol Number: 20130286

Date: 30 January 2017 Page 34 of 73

Table 3. Schedule of Assessments

		Double-Blind Period				Open-Label Period	
Study Day / Timepoint	Screening 4 (± 1) weeks	Day 1	Week 12 ± 3 days	Week 20 ± 3 days	Week 24 ± 3 days ^a	Week 36 ± 7 days	EOS Week 52 ± 7 days
Urinalysis	Х	Х	Х		Х	Х	Х
Hematology	Х	Х	Х		Х	Х	Х
Serum pregnancy, ^e urine pregnancy , ^e FSH/LH/estradiol ^f	Х	Х	х	х	х	х	Х
HbA1c	Х		Х		Х	Х	Х
Biomarkers (blood)		Х	Х		Х		X
Anti-evolocumab antibodies		Х	Х		Х	Х	Х
Investigational Product							
IP dispensing		Х	Х		Х	Х	
IP reconciliation			Х	Х	Х	Х	Х
IP administration (every 4 weeks) ^g		Х	х	Х	Х	Х	

Page 2 of 2

ApoA1=apolipoprotein A-I; ApoB=apolipoprotein B; CD4=cluster of differentiation 4; EOS=end of study; FSH=follicle-stimulating hormone; HbA1c=hemoglobin A1c; HIV=human immunodeficiency virus; IP=investigational product; LH=luteinizing hormone; Lp(a)=lipoprotein(a);

^a At week 24, final double-blind period assessments will be conducted, and the first dose of open-label study drug will be administered.

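### The rule for partial adverse event start dates makes no exception for the first open-label dose, so events that began on open-label evolocumab can be filed in the double-blind period, or in neither period

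*SAP*

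**What the plan says.** SAP 9.3.3 applies imputation only to dates that remain incomplete after querying: once the "issue is queried, if the date is still incomplete with year only or year and month only, the start date will be imputed" under Table 1. A missing day becomes the 1st, with the exception "Default to Study Day 1 if an event starts the same year and month as Study Day 1". A missing day and month becomes 1 January, with the exception "Default to Study Day 1 if an event started the same year as Study Day 1". Table 1 does not mention the first open-label dose.

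SAP 6.3 splits events by start date. "Double-blind TEAEs are those that start before the earlier of last dose date of double blind" "IP + 28 days and first dose date of open-label IP". On the other side, "Open-label TEAEs are those that start on or after the date of first dose of open-label IP".

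The eCRF question cited in SAP 9.3.3 is "Did event start before first dose of investigational product". It refers to the first dose of any study product.

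Both sides of the boundary meet at one visit (Protocol 7.1, Table 3, footnote a): "At week 24, final double-blind period assessments will be conducted, and the first dose of open-label study drug will be administered". From then on every continuing subject receives evolocumab. SAP 10.6.1 tabulates adverse events by actual treatment group, with double-blind events in the primary analysis and open-label events in the final analysis.

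**The concern.** The trial has two treatment boundaries: the first double-blind dose and the first open-label dose. Table 1 protects the first and ignores the second. Because imputation always moves a date back, to the start of the month or year or to Study Day 1, a partial date near the second boundary tends to move from open-label to double-blind.

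For a subject randomised to placebo, an event that began on evolocumab is then tabulated under placebo, in the only randomised safety comparison in the study. The serious, fatal and withdrawal tables rest on the same definition. The primary snapshot waits until the last subject has finished or left the double-blind period, so earlier enrolees may already have open-label events in the database by then.

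**Working it through.** The documents state no figure for this point, so there is none to reproduce. The check applies the two rules as written.

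**Inputs**
- Nominal schedule, in days after Study Day 1: last double-blind dose at +140 (week 20), first open-label dose at +168 (week 24), end of study at +364 (week 52).
- Imputation: SAP Table 1. Period assignment: SAP 6.3.
- Visit window for weeks 20 and 24: ± 3 days (Protocol Table 3).
- Assumptions: Study Day 1 takes each of 365 consecutive dates once, and onset days are uniform over the period.

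**Worked example**
- Study Day 1 is 15 January 2018. Last double-blind dose is 4 June and first open-label dose is 2 July. The double-blind cut-off is min(4 June + 28 days, 2 July) = 2 July.
- An event of 12 July recorded as July 2018 is imputed to 1 July, before 2 July: double-blind.
- An event of 20 November recorded as 2018 is imputed to 15 January: double-blind.
- Now take the week 20 dose 3 days early (1 June) and the week 24 dose 3 days late (5 July). The cut-off is min(1 June + 28 days, 5 July) = 29 June. The July 2018 event is again imputed to 1 July. That is not before 29 June and not on or after 5 July, so the event is in neither period.

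**Day missing, event in the open-label start month (nominal schedule)**
- A dose on day d of a month of length L leaves L − d + 1 open-label onset days in that month. Summed over d, this is L(L + 1)/2.
- Over the year: 7 × 496 + 4 × 465 + 406 = 5,738 onset days.
- Only a dose on the 1st keeps its events open-label. Those months contribute 365 days, and 365/5,738 = 6.4%.
- The rest become double-blind: 5,373/5,738 = 93.6%.
- As a share of all open-label onset days: 365 × 196 = 71,540, and 5,373/71,540 = 7.5%.

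**Year only (nominal schedule)**
- Enumerating the same 71,540 onset days, 73.0% are imputed into the double-blind period.

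**Week 20 dose 3 days early, week 24 dose 3 days late; day missing, start month**
- 59.9% double-blind, 33.8% in neither period, 6.4% open-label.

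**Effect on the comparison**
- Suppose a fraction r of subjects in each arm has an open-label event moved back. With about 300 and 150 subjects, the counts rise by 300r and 150r. Both incidences rise by r (300r/300 and 150r/150), and the absolute difference is unchanged.
- If some of those subjects already had the event, each incidence p rises by r(1 − p), assuming independence. The difference becomes (pE − pP)(1 − r), which is almost unchanged for small r.
- The risk ratio becomes (pE + r)/(pP + r), which is closer to 1 than pE/pP.

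**Does another rule close the gap?**
- The eCRF question settles whether an event is treatment-emergent. It does not settle which period the event belongs to.
- SAP 10.1 excludes data after the first open-label dose from the primary dataset, but it has no rule for partial dates. The only complete start date available is the imputed one.

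**The case against.** The strongest reply is that this hardly matters. Incomplete dates are queried first, and SAP 9.3.1 commits to pursuing missing and partial data before lock. A month-only date matters only in the calendar month of the open-label dose, and year-only dates should be rare after querying. Safety is summarised descriptively, so no test is affected. Overall treatment-emergent status rests on the eCRF question and does not change. All of this stands and keeps the point minor. It does not supply a rule for the dates that remain.

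A reader might also infer more than the documents support:
- **That every such event goes to double-blind.** It does not: a dose on the 1st keeps the event open-label, and off-schedule dosing can place it in neither period.
- **That placebo is penalised twice as heavily**, because one subject is 1/150 = 0.67 points of placebo incidence against 1/300 = 0.33 points of evolocumab incidence. That contrast only reflects 2:1 allocation. At equal per-subject rates, twice as many evolocumab subjects are affected and the increments match. A subject already counted for a term adds nothing.
- **That the randomised difference is narrowed.** On the absolute scale this would need newly switched placebo subjects to have more partially dated events than subjects continuing evolocumab. Nothing in the documents shows that.

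**Conclusion.** The gap is real and minor. Followed as written, Table 1 and SAP 6.3 together usually file an open-label event with an unresolved partial date in the month or year of the first open-label dose under double-blind, and sometimes under neither period. The certain harm is mislabelling: events that began on evolocumab appear under placebo for former placebo subjects, or drop out of both period tables. A risk ratio is pulled toward 1, while the absolute difference need not shift.

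The percentages assume uniform onset and, except where stated, an on-schedule subject. They describe what happens to a partial date of each kind and do not predict event counts. The number of unresolved partial dates is not given in the documents and is probably small after querying.

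**What to change.** Add an exception to Table 1 for events flagged as starting after the first dose of study product, and state that it takes precedence over the Study Day 1 exception. Precedence is needed because both apply to a year-only date when the two doses fall in the same year. If the known month (or year) is that of the first open-label dose:

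- classify the event as double-blind when collected data show that it began before that dose, for example a resolution date before the dose, or first entry in the eCRF at or before the week 24 visit;
- otherwise impute the start to the first open-label dose date (TR02SDTM).

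The tie-breaker is essential. A bare default to the open-label dose would reverse the error: 5,373 of 365 × 168 = 61,320 double-blind onset days (8.8%) would move to open-label for month-only dates, and about 77% for year-only dates. Resolution date is among the adverse event attributes in Protocol 9.2.2.1. The recording visit is not, so the sponsor should confirm that the time of first eCRF entry can be retrieved.

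List every adverse event whose period depends on an imputed date, and repeat the double-blind table with those events assigned the other way.

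Cost: one table row, some programming, one listing and one repeat table, all settled before the primary snapshot. The downside is that a few double-blind events reported late would move to open-label. The repeat table would show how much that matters.
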